NO response or without RODY designation will be contacted by a different letter (attached recruitment letter for RODY NO patients). If the colonoscopy was performed at MGH, after an adenoma is resected from a patient at MGH, all gastroenterologists routinely contact their patients by mail with the results of their pathology. The recruitment letter will be included with the pathology results when possible, or it will be sent separately after the pathology report. If the colonoscopy and polypectomy were performed at another hospital, the MGH gastroenterologist will confirm the prior diagnosis of an adenoma through review of pathology reports. Their treating MGH gastroenterologist, regardless of whether the physician is study personnel, will sign the letter. If no response is received to this recruitment letter within two weeks (10 business days) a follow-up phone call or email will be placed by a research assistant/study coordinator (phone script/sample email attached). In some cases, the treating gastroenterologist may approach the patient following the colonoscopy that identified a polyp if he/she feels the patient would be a good candidate for the study. In these cases, the patients may not receive a recruitment letter as the primary method of contact. Instead, they will be directly contacted by phone or email (see call script/sample email) from a member of the research team prior to mailing the letter (if requested). Potential participants will have additional opportunities to ask any questions by contacting an investigator or a trained research coordinator. If the participant is interested in participating, eligibility will be assessed by the study coordinator (see script) and confirmed by the investigator through an additional check of the patients' medical record (see "Investigator Representation for Review of Protected Health Information Preparatory to Research" form). If eligibility is confirmed, the patient will be scheduled for their initial study visit and registered with OnCore by the study staff. The informed consent form will be mailed to the patient prior to the initial visit so that he or she can read it in detail, if requested by the participant. Eligible participants will provide written informed consent at the baseline visit prior to participation in the study. The consenting process will be performed by one of the trial's clinical investigators.

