3.2 Exclusion Criteria

Participants who exhibit any of the following conditions at screening will not be eligible for admission into the study.

- 3.2.1 Currently using or have used any fish oil supplement at any dose more than once per week within the last month.
- 3.2.2 Regularly consuming more than three servings of fish per week.
- 3.2.3 History of allergic reactions attributed to fish or compounds of similar chemical or biologic composition to omega-3 fatty acid.
- 3.2.4 Diagnosis of inflammatory bowel disease, liver or kidney disease, bleeding diathesis
- 3.2.5 Any prior diagnosis of gastrointestinal cancer (including esophageal, small intestine, colon, pancreatic), or any diagnosis of other cancers (with the exception of non-melanoma skin) in which there has been any active treatment within the last three years.
- 3.2.6 Known diagnosis of Familial Adenomatous Polyposis (FAP) or Hereditary Non-Polyposis Colorectal Cancer (HNPCC, Lynch Syndrome).
- 3.2.7 Any adenoma that was not completely removed during previous colonoscopy.
- 3.2.8 Known bleeding tendency/condition (e.g. von Willebrand disease) or history of peptic ulcer or gastrointestinal bleed requiring hospitalization, endoscopic complications, or contraindication to colonoscopy.
- 3.2.9 Current use of anticoagulant therapies, including Heparin, Warfarin, Dalteparin sodium, Bivalirudin, Argatroban, Lepirudin, Heparin Sodium, Heparin/Dextrose, and an unwillingness or inability to discontinue anticoagulants.
- 3.2.10 Uncontrolled intercurrent illness including, but not limited to, ongoing or active infection, symptomatic congestive heart failure, unstable angina pectoris, cardiac arrhythmia, or psychiatric illness/social situations that would limit compliance with study requirements.

- 3.2.11 Inability or unwillingness to abstain from non-protocol use of fish oil supplements or to provide blood, urine or stool samples or colon biopsies during the study.
- 3.2.12 Participants who are receiving any other investigational agents.
- 3.2.13 Inability or unwillingness to swallow pills.
- 3.2.14 Pregnant or breastfeeding.

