5.5 General Concomitant Medication and Supportive Care Guidelines

Throughout the study, treating investigators may prescribe concomitant medications or treatments deemed necessary to provide adequate supportive care. However, participants may *not* receive:

- Other investigational agents;
- Anticoagulant therapies, including Heparin, Warfarin, Dalteparin sodium, Bivalirudin, Argatroban, Lepirudin, Heparin Sodium, Heparin/Dextrose, and other anticoagulant therapies;
- Any supplements that contain EPA.

All prescribed and non-prescription concomitant medications that are ingested, applied, or injected on an ongoing basis from signing of the informed consent, as well as changes in such concomitant medications, and any new concomitant medication taken while the participant is on study, should be recorded in the medical record. Concomitant medications for medically significant adverse events, which are ongoing at the end of study treatment and considered related to study treatment, should be followed until the adverse event is resolved or considered stable.

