7.1 Expected Toxicities

AMR101 may produce a hypersensitivity reaction in individuals with known hypersensitivity to shellfish/fish. Because AMR101 contains ethyl esters of omega-3 fatty acid, patients taking other anticoagulants may be at risk to develop a prolonged bleeding time; the risk of active bleeding is unknown.

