9.1.2.2 Initial (baseline) Visit

At the initial visit, the study physician will obtain written, informed consent for the study as well as a standard clinical consent for a flexible sigmoidoscopy. Following OnCore registration, participants will be asked to complete with a study coordinator a brief lifestyle questionnaire as well as a nutritional survey on a research iPad via VioScreen™, a validated web-based dietary assessment tool developed by Viocare, Inc (See appendix for VioScreen security overview, the assessed food list, and sample screens).¹²¹ Patients will undergo measurements of height, weight, waist and hip circumference and provide a blood and urine specimen. A study gastroenterologist will then perform a flexible sigmoidoscopy, advancing to the level of the distal sigmoid colon. No more than a total of 24 mucosal biopsies will be taken from the rectum and sigmoid and immediately placed in collection tubes. In the MGH GI Unit, we routinely perform endoscopic biopsies regardless of concurrent AMR101 use, a practice consistent with recommended guidelines.¹²² A study of the safety of multiple endoscopic biopsies in research subjects from a National Institutes of Health series found that performing large numbers of endoscopic biopsies (mean number = 38.2 ± 15.6 biopsies per procedure) are “well tolerated and appears to have no more than minimal risk without appreciably increasing the risk of otherwise routine endoscopy.”¹²³ Furthermore, there is no statistically significant association between risk of complications and the number of biopsies, type of procedure (flexible sigmoidoscopy vs. colonoscopy), colonic location of biopsy, operator, or polypectomy.¹²³ The number of biopsies is also consistent with our existing study protocols and has never been associated with any adverse events (See: “Endoscopy Protocol: Tissue Specific Immunity Against HIV-1”; PI: [name], Ragon Institute). We have estimated that 24 biopsies will be necessary to complete the proposed analyses. The RNAseq experiments proposed require a minimum of 4 pinch biopsies for each sample. The additional biopsies will be required for validation experiments based on the results of genomic and metagenomic analyses using targeted sequencing approaches. Due to the small number of cells obtained from pinch biopsies and the input requirements for these assays, we may use tissue culture techniques to expand cell populations. This will allow us to perform these comprehensive analyses without additional burden to the participants (i.e. increasing tissue yields by using larger or more biopsies). During flexible sigmoidoscopy, stool will be aspirated through the endoscope or using a Roth net and snap-frozen. Following the visit, questionnaire data will be transferred to the Partners secure

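### Criterion 3.2.9 passes a current anticoagulant user who is willing and able to stop, yet 5.5 bars anticoagulants and the plan has no step between consent and biopsy at which stopping could happen

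*Combined protocol and SAP*

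**What the plan says.** **When exclusions are judged.** Section 3.2 opens: "Participants who exhibit any of the following conditions at screening will not be eligible for admission into the study".

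**The criterion.** 3.2.9 begins "Current use of anticoagulant therapies, including Heparin, Warfarin, Dalteparin sodium", names further agents, and closes with "Heparin/Dextrose, and an unwillingness or inability to discontinue anticoagulants". It gives no stop date and no interval off therapy.

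**The on-study rule.** The list in 5.5 of what participants may not receive includes "Anticoagulant therapies, including Heparin, Warfarin, Dalteparin sodium, Bivalirudin, Argatroban, Lepirudin, Heparin Sodium, Heparin/Dextrose, and other anticoagulant therapies". Section 5.8 lists receipt of anything on that list as a reason to take the participant off study.

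**The order of events.** Under section 3, the coordinator assesses eligibility and the investigator confirms it from the medical record; only then is the initial visit scheduled. On consent, section 3 says "Eligible participants will provide written informed consent at the baseline visit prior to participation in the study". Section 9.1.2.2, which describes that same visit, agrees: "the study physician will obtain written, informed consent for the study as well as a standard clinical consent for a flexible sigmoidoscopy". The sigmoidoscopy, with at most 24 biopsies, follows at that visit. The study calendar (section 10) puts consent, sigmoidoscopy and biopsies in one Initial Visit column. Section 5.1 places the first dose after that sigmoidoscopy. Section 5.2, Pre-Treatment Criteria, is marked not applicable.

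**The concern.** An eligibility criterion should not admit a person in a state that the treatment rules forbid unless the plan also says how and when that state is to end. Here the plan relies on the person discontinuing a prescribed drug but assigns the discontinuation to no visit, interval or responsible clinician.

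Two things are at stake. One is consent: a change to prescribed therapy made only to join the study would come before the person has signed anything. The other is safety: if the change is left until consent is signed, up to 24 research biopsies follow within the same visit. The endpoints are laboratory biomarkers, so the study offers no clinical measure that would offset either risk.

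**Working it through.** No figure in the plan bears on this point, so the check is a comparison of texts, followed by a bound on the number affected.

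**Step 1: how 3.2.9 reads.** The clause has two limbs joined by 'and': (A) current use, and (B) unwilling or unable to discontinue. Limb B has meaning only for someone to whom limb A already applies, so the natural reading is that exclusion requires A and B together.

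| Person at screening | A | B | Excluded by 3.2.9? | State allowed by 5.5? |
|---|---|---|---|---|
| Not using | no | n/a | no | yes |
| Using, will not or cannot stop | yes | yes | yes | not enrolled |
| Using, willing and able to stop | yes | no | **no** | **no, until stopped** |

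The third row is the problem.

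**Step 2: where stopping could fit.** The documented sequence is:

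1. Eligibility assessed and confirmed (section 3).
2. Initial visit scheduled (section 3).
3. Written consent at the visit (section 3; 9.1.2.2).
4. Questionnaires, measurements, blood and urine (9.1.2.2).
5. Sigmoidoscopy with up to 24 biopsies, same visit (9.1.2.2; calendar).
6. First dose (5.1).

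Steps 3 to 5 fall within one visit. Stopping between steps 1 and 3 comes before written consent. Stopping between steps 3 and 5 leaves only the hours of the visit. No section adds an intermediate visit. The consent form may be mailed in advance on request, but it is still signed at the visit, so mailing opens no gap.

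**Step 3: whether it would be recorded.** Section 5.5 records concomitant medications and changes to them from the signing of consent. A change made before that falls outside the record.

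**Step 4: how many people.** The documents give no prevalence of anticoagulant use. If 2% to 5% of the recruited population were users (assumption), then 0.02 × 80 = 1.6 to 0.05 × 80 = 4 people. That counts all users. The gap reaches only those who are both willing and able to stop. If 10% to 50% of users are (assumption), the range is 0.10 × 1.6 = 0.16 to 0.50 × 4 = 2 people. The true number is unknown.

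**Step 5: effect on the primary analysis.** Section 13.7 excludes those who never start therapy or do not return for the final sigmoidoscopy. Section 13.7.2 keeps everyone who completes that procedure, whatever their compliance with study drug. Removal under 5.8 leads to loss only if the person does not return.

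**The case against.** The best reply is that 3.2.9, 5.5 and 5.8 fit together: a willing user stops, stays off, and is removed if they restart. On that view only a timing detail is missing. This is fair as far as it goes, since the three rules can be obeyed together. What it leaves open is that, with the visit order as written, they can be obeyed only by a change of therapy before consent or with no stated interval before biopsy. The visit sequence creates the difficulty, and more detail in 3.2.9 alone would not remove it.

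It can also be said that a course of treatment might end for clinical reasons between screening and the visit. That person meets no conflict, so not every willing user is affected.

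A reader might infer more than the documents support:

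- **That such a person is necessarily biopsied while anticoagulated.** This depends on how quickly an agent clears. The documents give no clearance times, and these would vary by agent.
- **That 7.1 shows a hazard at the baseline biopsies.** The sentence "patients taking other anticoagulants may be at risk to develop a prolonged bleeding time" concerns anticoagulants taken together with AMR101, and the first dose comes after the baseline sigmoidoscopy.
- **That 3.2.9 covers fewer drugs than 5.5.** Section 5.5 ends "Heparin Sodium, Heparin/Dextrose, and other anticoagulant therapies" and 3.2.9 has no such ending, but 3.2.9 introduces its agents with 'including', so its list is open. The difference is editorial.
- **That anticoagulant status goes unchecked before the visit.** Section 3 describes a pre-visit check against the medical record, and section 4.1 requires a protocol-specific eligibility checklist. The check largely exists; the criterion it applies is the problem.
- **That affected participants drop out of the primary analysis.** Under 13.7 and 13.7.2 this is not automatic.

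**Conclusion.** The point holds as a gap in participant safety and consent order. A current anticoagulant user who is willing and able to stop passes 3.2.9 in a state that 5.5 prohibits, and the plan offers no place after consent and before biopsy for that state to change.

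This rests on reading 'and' in 3.2.9 as joining two conditions. If the sponsor meant two separate exclusions, the sentence is ambiguous on a safety criterion and still needs rewording.

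The number affected is not known from the documents. A few of 80 is an upper bound under an assumed prevalence, and the figure is likely smaller because only willing and able users count. The effect on the primary analysis is nil or minor, so the case for amendment does not rest on power or bias.

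**What to change.** Reconcile 3.2.9, 5.5, 5.8, the baseline-visit order in 9.1.2.2 and the study calendar so that two things are true:

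1. A person who passes eligibility cannot be in a state that 5.5 prohibits at the first biopsy or the first dose.
2. No change of prescribed therapy made for the study is needed before written consent.

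Which clinical rule achieves this is for the sponsor and the treating physicians; this review proposes none. Using the same agent wording in 3.2.9 and 5.5 would be tidy but is editorial only. The existing eligibility checklist should then carry the reworded criterion.

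The cost is a wording amendment. Depending on the rule chosen, a few otherwise eligible people may not be enrolled.

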3.3 Inclusion of Women and Minorities

Women and minorities will be eligible for this study without alteration in eligibility criteria. Enrollment of these underrepresented populations to this trial will be encouraged.

4. REGISTRATION PROCEDURES

4.1 General Guidelines for DF/HCC Institutions

Institutions will register eligible participants in the Clinical Trials Management System (CTMS) OnCore. Registrations must occur prior to the initiation of protocol therapy. Any participant not registered to the protocol before protocol therapy begins will be considered ineligible and registration will be denied.

An investigator will confirm eligibility criteria and a member of the study team will complete the protocol-specific eligibility checklist.

The study staff will register the participant in OnCore.

Following registration, participants may begin protocol-specific therapy and/or intervention. Issues that would cause treatment delays should be discussed with the Overall Principal Investigator (PI). If the subject does not receive protocol therapy following registration, the subject must be taken off-study in the CTMS (OnCore) with an appropriate date and reason entered.

4.2 Registration Process for DF/HCC Institutions

Applicable DF/HCC policy (REGIST-101) must be followed.

4.3 General Guidelines for Other Investigative Sites

N/A.

4.4 Registration Process for Other Investigative Sites

N/A.

5. TREATMENT PLAN

5.1 Treatment Regimen

After study registration, eligible participants will be assigned unique study identification numbers. The investigator will contact the MGH Research Pharmacy for drug dispensation. The MGH Research Pharmacy will dispense study capsules, obtained from Amarin Pharma (Bedminster, NJ), containing 0.5-gram of AMR101. The assigned dosage will not change over the course of the study unless dose reduction is indicated (See Section 6). The first dose of the study medication will be given to patients after the initial flexible sigmoidoscopy. Participants will be expected to take 4 capsules orally, twice a day, until the return for their final visit (minimum 8 weeks, maximum 12 weeks). The final visit, 8-12 weeks from the baseline visit, will be scheduled during or before the baseline visit. The MGH Research Pharmacy will assign the participant three bottles of AMR101 each containing 240 capsules (12 weeks, 8 capsules/day) and participants will return any unused capsules and the bottle to the study staff at their final visit. The bottle will be labeled with their participant ID. The participant number must be recorded on the drug dispensation form and in the participants case report form (CRF). These numbers are unique to each participant and must not be re-assigned. Remaining capsules will be counted as a measure of compliance, the number recorded and then the remaining capsules will be immediately destroyed. Weekly calls will be used to monitor adherence and adverse events. Patients who initiate fish oil supplements during the study will be withdrawn and an exit visit performed.

Compliance will be assessed based on drug diary and pills counts, as well as blood measurement of EPA levels. Reported adverse events and potential risks are described in Section 7. No investigational or commercial agents or therapies may be administered with the intent to treat the participants. The principal investigator will review subjects' data periodically throughout the duration of the study for quality, validity and integrity assurance and for adherence to the IRB

approved protocol and will address any data-related issues that might arise.

5.2 Pre-Treatment Criteria

N/A

5.3 Agent Administration

5.3.1 AMR101

Participants will self-administer eight AMR101 capsules by mouth (4 capsules twice a day), and will be instructed to keep a drug diary. The dose should be taken with food and a full glass of water. If a daily dose is missed, the dose should be skipped. A dose is considered missed if more than 24 hours has elapsed since the prior dose.

5.4 Definition of Dose-Limiting Toxicity (DLT)

N/A

5.5 General Concomitant Medication and Supportive Care Guidelines

Throughout the study, treating investigators may prescribe concomitant medications or treatments deemed necessary to provide adequate supportive care. However, participants may *not* receive:

- Other investigational agents;
- Anticoagulant therapies, including Heparin, Warfarin, Dalteparin sodium, Bivalirudin, Argatroban, Lepirudin, Heparin Sodium, Heparin/Dextrose, and other anticoagulant therapies;
- Any supplements that contain EPA.

All prescribed and non-prescription concomitant medications that are ingested, applied, or injected on an ongoing basis from signing of the informed consent, as well as changes in such concomitant medications, and any new concomitant medication taken while the participant is on study, should be recorded in the medical record. Concomitant medications for medically significant adverse events, which are ongoing at the end of study treatment and considered related to study treatment, should be followed until the adverse event is resolved or considered stable.

5.6 Criteria for Taking a Participant Off Protocol Therapy

Duration of study drug administration will be at minimum 8 weeks and no more than 12 weeks from the initial visit. Duration of administration will equal the number of days between initial and final visit. Study drug administration will continue until the final visit or until one of the following criteria applies:

- Intercurrent illness that prevents further administration of study drug

- Unacceptable adverse event(s)
- Participant demonstrates an inability or unwillingness to comply with the oral medication regimen and/or compliance requirements
- Participant decides to withdraw from the protocol therapy
- General or specific changes in the participant's condition render the participant unacceptable for further treatment in the judgment of the treating investigator
- Participant self-administers any additional non-study fish oil supplements.

Participants will be removed from the protocol therapy when any of these criteria apply. The reason for removal from protocol therapy, and the date the participant was removed, must be documented in the eCRF. Alternative care options will be discussed with the participant.

When a participant is removed from protocol therapy and/or is off of the study, the relevant Off-Treatment/Off-Study information will be updated in OnCore.

In the event of unusual or life-threatening complications, participating investigators must immediately notify the Overall PI, [name] at [contact] or [contact]

